informed consent in the UC Riverside laboratory within 1 month of first ascent (Summer 2025). Participants then complete medical history and basic physical screening. At this time, they are randomly assigned to a treatment group (*i.e.* Group A taking AZ on trip 1 and placebo on trip 2), maintaining age and sex ratios across groups. Participants will be asked to begin taking their assigned treatment as indicated 2 days before each ascent (125 mg twice daily for AZ).¹⁴ On the morning of ascent, participants arrive at the lab at 6:00 am and fasting peripheral venous blood samples will be collected by a licensed phlebotomist or physician. Participants then travel to Barcroft Station (3800 m elevation) *via* vehicle (6 -7 hours). Over three days at high altitude, participants complete morning fasting blood draws, morning and evening AMS questionnaires (Lake Louise)¹⁵, and morning and evening physiological measures (blood pressure, heart rate, SpO₂). On the second day at high altitude, ventilatory chemoreflex measures will be collected as previously described by our group.¹⁶ WatchPAT sleep kits will be used to characterize nocturnal hypoxic burdens, oxygen desaturation indices, and apnea hypopnea indices as previously described by our group.¹⁷ Following descent, participants complete 1-week and 1-month follow-up visits to determine the long-term effects of high-altitude exposure on immune phenotypes.

100 µl of whole blood will be fixed and stained immediately on-site at each timepoint for flow cytometry analysis at UC Riverside within 3 days of sample collection. We will also conduct complete blood counts on-site. 20 ml of EDTA-treated blood will be utilized for plasma collection and isolation of peripheral blood mononuclear cells by density gradient centrifugation. Isolated immune cells will be immediately frozen and stored in liquid nitrogen for transport to UC Riverside using a novel protocol optimized by our group for cryogenically storing viable cells in remote field locations.⁷ Upon return to sea level, immune cells will be cultured in the presence or absence of several stimulants including bacterial lipopolysaccharide (LPS) and R848 (Resiquimod, stimulating the antiviral response). Following stimulation, we will collect culture

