supernatants and measure expression of inflammatory factors using Legendplex multi-plex cytokine panels as previously described by our group.¹⁸ These panels allow simultaneous measurement of many key inflammatory mediators including 13 inflammatory cytokines, 12 markers of vascular inflammation, and 13 anti-viral response factors. We will also conduct additional functional assays, including bacterial killing and cell migration assays. Plasma cytokine levels will also be measured via Legendplex. All cell culture assays will be conducted in triplicate with downstream cytokine profiling in duplicate.

b. Power calculations: Sample sizes are based on power calculations targeting 80% power to detect significant differences across sea level and high altitude at $\alpha = 0.05$. Calculations were performed using *pwr* in R and are based on previously published data or our own preliminary work. A sample size of 14 is required to detect a significant shift from classical to intermediate monocyte subsets after 1 day at high altitude with an effect size in our prior studies of 0.46.⁷ Additionally, a sample size of 10-36 is required to detect significant correlations between AMS score and classical ($R^2 = 0.79$) or non-classical monocytes ($R^2 = 0.45$). Finally, we previously identified elevations in inflammatory response genes after 1-3 days at high altitude with a sample size of 17.¹ Thus, we predict we are well powered with a sample size of 20 individuals (cross-over design) to detect significant changes in immune phenotypes at high altitude as well as correlations between immune cell distributions and AMS scores. This sample size is also consistent with other studies examining the efficacy of AZ for AMS treatment.¹⁹

c. Data analysis plan: Treatments will be assigned by a third party and all study team members and participants will be blinded. Data analysis will be conducted by a research team member who is blinded to participant treatment, demographic information, and day of sample collection. All samples and physiological data will be deidentified and coded. To determine if AZ treatment is linked to reduced inflammatory cytokine expression and reduced levels of pro-inflammatory

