innate immune cell subsets (Aim 1), we will first utilize two-way repeated measures ANOVA to compare plasma cytokine expression and cell distributions across study days and treatments. To determine the impact of AZ treatment on innate immune cell function (Aim 2), we will use a three-way ANOVA to examine cell cytokine secretion across study days, treatments, and pre/post cell stimulation. Significant main effects will be further evaluated with post-hoc Tukey's HSD tests, and we will verify our data meets all required test assumptions. We will carefully examine impacts of sex, age, BMI and other demographic factors on outcomes using mixed linear models. WatchPAT data will be analyzed according to the American Academy of Sleep Medicine criteria by a qualified sleep technician and ventilatory parameters will be analyzed as described previously.^{16,20–22} To determine if these parameters are associated with our immune and AMS outcomes, we will conduct mixed linear models with trip, day, treatment, and sex, as covariates.

d. Timeframe: This study will take place in the summer of 2025. Participants will be recruited in the month prior to study start, and work will be conducted over two expeditions. Participants will complete baseline testing within one week of ascent. They will then arrive on the morning of ascent for sea-level blood sampling, be driven to Barcroft Station over 6 hours in vans, and will remain at the station for 3 nights (4 days) during each visit. The group will then return to sea level and a follow-up appointment will be completed 1 week and 1 month following return. The second trip will take place 1-2 months after the first. Flow cytometry and multiplex cytokine panel tests will be conducted immediately after each trip, and cell functional assays will be completed within 2 months of return. Final data analyses will be complete over the following 2 months in time for an abstract submission to the American Physiology Summit by the deadline in Fall 2025 and attendance of the 2026 Winter Conference of the Wilderness Medical Society. The manuscript resulting from this work will be submitted for publication in *Wilderness & Environmental Medicine* by Summer 2026.

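### The Aim 1 treatment comparison is fixed as a two-way repeated-measures ANOVA, which in its classical form loses, per outcome, any participant with one missing sample and has no trip term; a mixed model, already planned elsewhere, would be the better main analysis.

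*Protocol*

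**What the plan says.** Protocol section C.c (Data analysis plan) sets the Aim 1 method: "we will first utilize two-way repeated measures ANOVA", with study day and treatment as the two factors, applied to the plasma cytokines and the immune-cell distributions. Trip is not among the factors.

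The number of cells per person follows from the sampling schedule:
- Sea level (C.d, Timeframe): "They will then arrive on the morning of ascent for sea-level blood sampling".
- Altitude (C.a, Study Design): "Over three days at high altitude, participants complete morning fasting blood draws".
- After descent (C.a): "participants complete 1-week and 1-month follow-up visits to determine the long-term effects of high-altitude exposure on immune phenotypes". The protocol does not say whether these visits enter the Aim 1 ANOVA.
- All of this happens on each of two trips, 1 to 2 months apart (C.d).

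Mixed models appear twice in C.c. One use is to examine "impacts of sex, age, BMI and other demographic factors on outcomes using mixed linear models". The other links sleep and ventilatory parameters to the immune and AMS outcomes, with trip, day, treatment and sex in the model. Neither is assigned the main Aim 1 treatment comparison.

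Section C.b (Power calculations) justifies 20 participants without mentioning lost samples or dropout.

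**The concern.** A classical within-subject ANOVA on day by treatment needs a full grid for each person, and standard software usually excludes a participant with one empty cell. With 8 to 12 cells per person, a small loss rate per sample becomes a much larger loss of participants. The samples come from a remote station on two expeditions, so some loss is foreseeable.

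Two things are at stake in a 20-person trial. The first is precision: the three to seven or more other samples from an incomplete participant are discarded for that outcome. The second is validity: if people who feel worse at altitude miss more draws, the complete cases are a selected group, and AMS is part of the study hypothesis.

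The missing trip term adds to this. Write the trip 1 minus trip 2 difference as p. A person who takes AZ first has an expected AZ-minus-placebo difference of the treatment effect plus p; a person who takes placebo first has the treatment effect minus p. With equal sequence groups p cancels from the mean but inflates the error. With unequal groups it does not cancel, and exclusions can make the groups unequal.

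**Working it through.** **The plan's own sample-size figure.** C.b gives 14 for a monocyte shift with effect size 0.46, 80% power and alpha 0.05. Reading 0.46 as Cohen's f in a one-way ANOVA with four levels (sea level plus three altitude days) gives n = 13.9, hence 14. That reading is inferred, because the type of effect size is not stated. The figure concerns change with altitude, not AZ against placebo, so the gap between 14 and 20 is not a margin for the treatment comparison.

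**Inputs.** N = 20 (C.b). Samples per person: m = (1 + 3) x 2 = 8, or m = (1 + 3 + 2) x 2 = 12 with both follow-up visits (C.a, C.d). The loss rate q per sample is not in the documents; 2%, 5% and 10% are assumed.

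**Complete participants under independent loss**, 20 x (1 - q)^m:

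| q | m = 8 | m = 12 |
|---|---|---|
| 2% | 17.0 | 15.7 |
| 5% | 13.3 | 10.8 |
| 10% | 8.6 | 5.7 |

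**How many lost samples cost a third.** A third of 20 is 6.7, so at least 7 participants must each lose one. With L samples lost at random out of 160, the expected number excluded is 20 x [1 - C(152, L)/C(160, L)]:
- L = 3: 2.9 excluded (14%)
- L = 5: 4.6 excluded (23%)
- L = 7: 6.1 excluded
- L = 8: 6.9 excluded, 13.1 left

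A loss of a third corresponds to q = 1 - (2/3)^(1/8) = 4.9% with 8 samples, or 1 - (2/3)^(1/12) = 3.3% with 12.

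**Power.** Take a paired comparison of the mean of the three altitude mornings, two-sided alpha 0.05, and a true effect of 0.66 SD of the paired difference. At n = 20 the noncentrality is 0.66 x sqrt(20) = 2.95 on 19 df, which gives 80%. With 8 samples and independent loss:

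| q | Complete cases | All available samples |
|---|---|---|
| 2% | 73% | 80% |
| 5% | 60% | 79% |
| 10% | 39% | 77% |

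These are simulated (8,000 runs). Averaging the noncentral-t power over the binomial number of completers gives 72%, 59% and 39%, in agreement. The right-hand column averages whatever altitude mornings are present; it does not fit the full mixed model. It depends modestly on the correlation between mornings within a trip: at 10% loss it runs from about 75% to 79% for correlations of 0.1 to 0.9.

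**Clustered loss.** If the same share is lost as whole trips, the number complete is 20 x (1 - q)^2 = 19.2, 18.05 and 16.2, and paired power is about 78%, 75% and 70%.

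**Trip term.** With nA and nB completers in the two sequences, the mean paired difference is the treatment effect plus p x (nA - nB)/(nA + nB). As an illustration, 13 completers split 8 to 5 would carry 3/13 = 0.23 of p into the treatment estimate.

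**The case against.** The strongest reply is that the protocol never says incomplete participants are dropped. It is silent on missing samples, and a missing-sample rule commonly belongs in the statistical analysis plan, which is not shown. That stands, and the silence is not criticised here. The point is that the protocol has already named a method that, in its classical form, handles incomplete records badly.

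Several stronger readings are tempting and are not supported:

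- *A few lost tubes would cost a third of the sample.* Three to five lost samples cost about 14% to 23%; a third takes at least 7, each from a different participant. No loss rate is given, so any percentage is an assumption.
- *One failed sample removes all of a person's data.* Exclusion is per outcome. Under C.a, flow cytometry uses a separately fixed and stained 100 µl of whole blood, while plasma comes from the EDTA blood. A failed stain leaves plasma cytokines intact, and a failed thaw affects only the cultured cells of Aim 2. Only a missed draw touches every outcome.
- *Aim 2 has the same defect.* The protocol says "we will use a three-way ANOVA to examine cell cytokine secretion across study days, treatments, and pre/post cell stimulation" and does not call it repeated measures. An ordinary factorial ANOVA does not drop a person for one empty cell, so the mechanism is not shown there.
- *Mixed models are planned only for demographic covariates.* C.c also plans them for immune outcomes with trip, day and treatment, although aimed at associations with sleep and ventilation.

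The objection about the loss pattern also stands. Independent loss spreads missing samples over the most people and is close to the worst case. Missed trips or early descents cluster, and a person with no data from one trip gives a mixed model little within-person treatment information.

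**Conclusion.** The concern holds for Aim 1 as a choice of method. The named ANOVA is prone to complete-case exclusion, it omits trip in a two-period cross-over, and a better model class is already in the same section. The size is conditional. With scattered loss of about 5%, roughly a third of participants would be excluded for the affected outcome (more with 12 samples) and power would drop by about 20 points. With loss confined to whole trips, the drop at 5% is about 5 points and switching models recovers little of it. All power figures rest on assumed loss rates, an assumed 0.66 SD effect and a two-sided paired comparison. Bias from selective missingness is possible but cannot be sized from the protocol. This is worth correcting before the data are analysed; it does not invalidate the design.

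**What to change.** In C.c, make the main Aim 1 treatment comparison a linear mixed model for each outcome:

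- participant as random effect, and treatment, day, treatment-by-day and trip as fixed effects;
- an allowance for samples from the same person and trip being more alike, for example a participant-by-trip random effect, so that treatment is not tested against day-to-day error alone;
- REML on all available samples, with a small-sample degrees-of-freedom correction such as Kenward-Roger;
- a statement of whether the 1-week and 1-month visits enter the model.

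Keep the repeated-measures ANOVA as a sensitivity analysis. No extra participants, samples or model class are needed, so the cost is wording. The statistical price is that inference rests on samples being missing at random given the data in the model; recording the reason for each lost sample would help a reader judge that.

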A. Introduction and Background: Acetazolamide (AZ) is a highly effective treatment for acute mountain sickness (AMS) at high altitude.^{8,9} AZ mitigates AMS through its activity as a renal carbonic anhydrase inhibitor, which decreases blood pH and stimulates ventilation to improve oxygen delivery to tissue.^{9,10} However, AZ also demonstrates immune modulatory properties, with most evidence examining this in lung tissue to investigate the impact on pulmonary hypertension in animal models.^{11,13} Our group and others show that high-altitude exposure results in an acute pro-inflammatory response and activation of the innate immune system, which some predict contributes to the onset and severity of AMS.^{1,7} Therefore, the anti-inflammatory properties of AZ may play a key role in modulating AMS symptoms independent of ventilatory stimulation. However, prior work has examined the impact of AZ on only a select few inflammatory mediators, and the impact of AZ on immune function has never been evaluated.

B. Hypothesis and specific aims: Our goal is to determine if AZ mitigates the pro-inflammatory innate immune response during high altitude travel. We hypothesize that AZ improves AMS symptoms, in part, by reducing systemic hypoxia-induced inflammation and reducing the activation of innate immune cells (monocytes and neutrophils). We will test this hypothesis with the following experimental aims: (**Aim 1**) Determine if AZ treatment during high altitude exposure blunts plasma inflammatory cytokine expression and levels of circulating pro-inflammatory innate immune cell subsets; (**Aim 2**) Determine if AZ treatment during high altitude exposure modulates immune cell function (innate inflammatory responses to bacterial and viral stimuli, cell migration, and bacterial killing efficacy).

C. Study design and methods:

a. Study Design: This is a double blind, randomized, cross-over, placebo-controlled trial.

Participants (N=20) will be recruited by word of mouth and advertising, and complete written

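### The Aim 1 and Aim 2 ANOVAs compare acetazolamide with placebo without a trip (period) term, so any trip or batch difference enters the treatment main effect

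*Protocol*

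**What the plan says.** All references are to the Protocol, Section I.C.

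- **Design (a. Study Design).** "This is a double blind, randomized, cross-over, placebo-controlled trial" Each of 20 participants takes AZ on one trip and placebo on the other. Assignment is random, "maintaining age and sex ratios across groups"; equal sequence sizes are not stated.
- **Aim 1 (c. Data analysis plan).** A "two-way repeated measures ANOVA to compare plasma cytokine expression and cell distributions across study days and treatments".
- **Aim 2 (c. Data analysis plan).** A "three-way ANOVA to examine cell cytokine secretion across study days, treatments, and pre/post cell stimulation". Post-hoc Tukey tests follow significant main effects.
- **Demographics (c. Data analysis plan).** "We will carefully examine impacts of sex, age, BMI and other demographic factors on outcomes using mixed linear models" Trip is not named.
- **Sleep and ventilation (c. Data analysis plan).** Their association with immune and AMS outcomes is examined in "mixed linear models with trip, day, treatment, and sex, as covariates". This is the only model that names trip.
- **Assay timing (d. Timeframe).** "Flow cytometry and multiplex cytokine panel tests will be conducted immediately after each trip". The trips are 1-2 months apart.
- **Follow-up (a. Study Design).** Visits at 1 week and 1 month after descent are intended "to determine the long-term effects of high-altitude exposure on immune phenotypes".

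**The concern.** In a two-period crossover, treatment and period are separated only by comparing the two sequences. A model with day and treatment alone makes no such comparison. Whatever differs between the trips stays inside the AZ-placebo differences.

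A trip difference is plausible here for two reasons. Each person's AZ and placebo samples for flow cytometry and the multiplex panels are run in different sessions, so assay batch coincides with trip. The second ascent also falls 1-2 months after the first, while the protocol treats lasting immune effects of altitude as an open question.

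At stake is the power of the treatment main effect in a trial of 20 people and, if the sequences are unequal, the accuracy of the AZ estimate. This is not detail that the protocol leaves to an SAP. It fixes the factors of both analyses, and it names trip in a different model.

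**Working it through.** **The plan's own figure.** Section I.C.b gives n = 14 for a monocyte shift with effect size 0.46. It reproduces as a one-way ANOVA with Cohen's f = 0.46 and four groups (13.9 per group; power 80.3% at 14). It concerns sea level against altitude. No figure is given for AZ against placebo, so the effect below is an assumption.

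**Inputs.**
- From the protocol: N = 20, alpha 0.05, target power 80%.
- Assumed: a two-sided test; within-person AZ-placebo differences with SD 1; a true effect of tau = 0.66 SD, which gives about 80% power with a trip term at 10/10; and a trip difference pi of 0 to 1.0 SD (trip 1 minus trip 2).

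**Step 1: what the ANOVA tests.** In a two-way repeated-measures ANOVA, the treatment F equals the squared paired t on participants' mean differences. On simulated data both were 2.538. The main effect can therefore be studied through

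D_i = tau + s_i × pi + e_i,

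with s_i = +1 if AZ is taken on trip 1 and −1 if on trip 2.

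**Step 2: bias.** The mean of D is tau + pi × (n1 − n2)/20. The bias is 0 at 10/10, 0.1 pi at 11/9 and 0.2 pi at 12/8. For pi = 1.0 SD, that is 0.10 SD at 11/9 and 0.20 SD at 12/8.

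**Step 3: error variance at 10/10.** Without a trip term, the expected error mean square is multiplied by 1 + 20 pi²/19. For pi = 0.5 this is 1 + 5/19 = 1.26. For pi = 1.0 it is 1 + 20/19 = 2.05.

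**Step 4: power and type I error at 10/10.** Without a trip term, the t statistic has 19 df and its sum of squares is noncentral chi-square with noncentrality 20 pi². Integrating over that distribution gives:

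| Trip difference (SD) | Variance multiplier | Type I error | Power, no trip term |
|---|---|---|---|
| 0 | 1.00 | 5.0% | 80% |
| 0.25 | 1.07 | 4.4% | 78% |
| 0.5 | 1.26 | 2.9% | 72% |
| 0.75 | 1.59 | 1.5% | 62% |
| 1.0 | 2.05 | 0.6% | 49% |

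With a trip term (18 df), power stays at about 80%, type I error at 5% and bias at 0 in every row. If there is no trip difference, the term costs almost nothing: 79.7% power against 79.95% without it.

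**Step 5: type I error with unequal sequences, no trip term.** For pi = 0.5 and 1.0 it is 3.3% and 1.1% at 11/9, and 4.5% and 3.0% at 12/8. It passes 5% at 13/7 (6.6% and 7.5%) and at 14/6 (9.7% and 16.5%).

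**Step 6: the interaction.** Adding a constant trip shift of 0, 0.5, 1.0 or 1.5 to simulated data (20 people, four days) left the treatment-by-day F unchanged at both 10/10 and 12/8. Only the treatment F moved. A constant shift cancels when days are compared within a trip.

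**The case against.** The strongest reply is that Aim 1 asks whether AZ blunts the response to altitude. Each trip has its own sea-level sample, so the most direct test is the treatment-by-day interaction, which a constant trip shift does not touch. This stands, and it limits the figures above to the main effect. It does not remove the point, because the plan carries significant main effects into post-hoc tests. A trip effect that varies by day or is multiplicative would also reach the interaction.

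A reader might infer more than the documents support:

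- **That false positives are likely.** At 10/10, 11/9 and 12/8 the test stays below 5%. Nothing in the protocol suggests an imbalance as large as 13/7 or 14/6.
- **That a trip difference is certain, or that lasting effects are expected.** The protocol shows only that assays follow each trip and that long-term effects will be looked for. No size is given, and at zero nothing is lost.
- **That the ANOVA will drop people with a missing sample and so unbalance the sequences.** The protocol does not specify missing-data handling, which may be in an SAP.
- **That Aim 2 is batched by trip in the same way.** Per-trip timing is stated for flow cytometry and the panels. The cell functional assays are only to be finished within 2 months of return.
- **That this is the designated primary analysis.** The protocol says only that the ANOVA comes first.

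The sleep and ventilation models do relate immune outcomes to trip and treatment together. They condition on a sleep or ventilatory measure, so they are no substitute for the AZ comparison.

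**Conclusion.** The point holds for the treatment main effect in both aims and should be fixed. With equal sequences the harm is lost power and a conservative test, not bias: from 80% to about 78%, 72%, 62% or 49% for trip differences of 0.25, 0.5, 0.75 or 1.0 SD. With unequal sequences the AZ estimate is also biased, by one tenth of the trip difference at 11/9 and one fifth at 12/8.

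These sizes rest on an assumed trip difference and an assumed AZ effect of 0.66 SD, neither of which is in the document. They do not apply to the treatment-by-day interaction under a constant additive shift, so the omission does not by itself undermine the test of blunting. It is a stated analysis that is weaker than an alternative costing next to nothing.

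**What to change.** Replace both ANOVAs with a linear mixed model. The fixed effects are treatment, trip, sequence, day and treatment-by-day, with stimulation and its interactions added for Aim 2. The random effects are participant and participant-by-trip. Use all available samples.

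The cost is a change to the analysis wording and one residual degree of freedom for trip. The trip term removes additive period and batch differences. It does not remove carry-over that differs by treatment, and the text should say so.

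Running each participant's plasma from both trips on the same multiplex plates is optional and not part of this fix. It would exchange a plate difference for a storage-time difference of 1-2 months. It would also delay the trip 1 plasma results, against the Fall 2025 abstract deadline in Section I.C.d.

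### Aim 2 cytokine analysis: follow-up is tied to main effects, but the question of altered response to stimulation sits in the treatment-by-stimulation contrast, which the protocol does not name

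*Protocol*

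**What the plan says.** Protocol Section I, B (Hypothesis and specific aims) sets Aim 2 as finding out whether AZ "modulates immune cell function (innate inflammatory responses to bacterial and viral stimuli, cell migration, and bacterial killing efficacy"). Only the first item, the inflammatory response to stimuli, concerns cytokine secretion.

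Section I, C.a (Study design) describes the culture step: "immune cells will be cultured in the presence or absence of several stimulants including bacterial lipopolysaccharide (LPS) and R848". The unstimulated well is the reference against which a response can be read.

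Section I, C.c (Data analysis plan) gives the Aim 2 model as a "three-way ANOVA to examine cell cytokine secretion across study days, treatments, and pre/post cell stimulation". The next sentence gives the follow-up rule: "Significant main effects will be further evaluated with post-hoc" Tukey tests. The section names no interaction or contrast. It does not say which term decides Aim 2, and it does not define a response as a level, an increment or a fold change.

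**The concern.** With paired stimulated and unstimulated wells, a change in response means that the stimulated-versus-unstimulated difference is not the same on AZ as on placebo. That is the treatment-by-stimulation term. The main effects answer other questions:

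- Stimulation: do LPS and R848 provoke secretion? This says nothing about AZ.
- Study day: does secretion change over the trip? This says nothing about AZ either.
- Treatment: does AZ change secretion averaged over both kinds of well and all days?

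The only effect involving AZ that the written rule carries forward is therefore an average. If cells drawn on AZ secrete less in both wells by the same amount, the treatment effect can be significant and be reported as altered innate responsiveness when the increment has not moved. A common shift is plausible, since the study hypothesis is that AZ lowers systemic inflammation. Conversely, a significant interaction has no stated follow-up.

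**Working it through.** **The plan's own figure.** The protocol gives no power figure for Aim 2. The nearest is the sample size of 14 in Section I, C.b for a monocyte subset shift, "with an effect size in our prior studies of 0.46". A one-way ANOVA with f = 0.46, 80% power, alpha 0.05 and an assumed four groups gives 13.9 per group, so 14 can be reproduced. The test behind it is not stated (a paired t test with d = 0.46 would need 39.1), and it concerns neither treatment nor stimulation. It does not bear on what follows.

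**Inputs.** From the protocol: a "sample size of 20 individuals (cross-over design"), so 20 within-participant differences; alpha 0.05. Assumed: two-sided testing, the SDs, the correlation and the shifts.

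**Set-up.** For each participant let Ds and Du be the AZ-minus-placebo difference in stimulated and unstimulated wells, with SD 1 and k and correlation rho.

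- Main effect: M = (Ds + Du)/2, variance (1 + k² + 2·rho·k)/4.
- Interaction: I = Ds − Du, variance 1 + k² − 2·rho·k.
- Power: noncentral t, 19 df, critical value 2.093, noncentrality √20 × mean/SD.

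**Case 1: same shift in both wells, increment unchanged (k = 1).** Worked example, shift 0.5 and rho 0.5: M has mean 0.5 and SD √0.75 = 0.866, ratio 0.577, noncentrality 2.58, power 69%. I has mean 0, so it rejects 5%.

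| rho | 0 | 0.3 | 0.5 | 0.7 |
|---|---|---|---|---|
| Main effect, shift 0.3 | 44% | 35% | 31% | 28% |
| Main effect, shift 0.5 | 85% | 75% | 69% | 63% |
| Interaction, either shift | 5% | 5% | 5% | 5% |

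**Case 2: only stimulated wells lower, by 0.7.**

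| rho | 0 | 0.3 | 0.5 | 0.7 |
|---|---|---|---|---|
| k = 1: main effect | 56% | 45% | 40% | 36% |
| k = 1: interaction | 56% | 71% | 84% | 97% |
| k = 1/3: main effect | 80% | 74% | 70% | 66% |
| k = 1/3: interaction | 80% | 87% | 92% | 96% |

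The loss from using the main effect runs from nil to about 60 points at k = 1 and from nil to 30 points at k = 1/3. At k = 0.1 it is at most 10 points.

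**Case 3: three levels (none, LPS, R848), equal SDs, both responses lower by 0.7.** The main effect has mean 1.4/3 = 0.467 and variance (1 + 2·rho)/3. At rho 0 the ratio is 0.467/0.577 = 0.81, power 93%; at rho 0.3 power is 77%. A separate contrast for one stimulant has 56% and 71%, as in Case 2. Here the main effect is the more powerful test. At rho 0.5 the order returns: 68% against 84%.

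**Case 4: only unstimulated wells shift, by 0.7 (k = 1).** By symmetry with Case 2 the main effect rejects 56% to 36% and the interaction 56% to 97% as rho goes from 0 to 0.7. A test on stimulated wells alone stays at 5%.

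**The case against.** The strongest reply is that the plan does not say what a reader might infer from it, namely that the treatment main effect is the test of Aim 2. That is correct. Crossing stimulation with treatment is the usual way to obtain their interaction, and a three-way ANOVA normally contains it. Treatment and pre/post stimulation have two levels each, so Tukey tests on those main effects add nothing to the F test, which suggests loose wording rather than a decision to ignore interactions. Naming the decisive contrast is also often left to a statistical analysis plan, and none is at hand. What remains is that the protocol is not silent: it states which effects go forward, and those are not the ones its aim needs.

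A second reply is that the protocol does not define response. If it means the level secreted under LPS or R848, a common shift does change it, so the 28% to 85% is not an error rate of the plan. This also stands in part. The figure shows that the main effect cannot tell two explanations apart; which of them counts as altered function has to be stated.

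A third reply concerns the remedy. A reader might infer that the interaction protects when only spontaneous secretion moves. It does not: the increment then changes and the interaction rejects at least as often as the main effect (Case 4). It protects only against a shift common to both wells.

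**Conclusion.** The point holds in limited form. The cytokine part of Aim 2 is about "innate inflammatory responses to bacterial and viral stimuli", while the written follow-up rule covers main effects only and no treatment-by-stimulation contrast is named. Whatever the SDs or correlation, the treatment main effect cannot distinguish a blunted response from a shift common to both wells. Under equal SDs, rho 0 to 0.7 and N = 20, common shifts of 0.3 to 0.5 SD make it significant 28% to 85% of the time with the increment unchanged, against 5% for the interaction.

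A reader might also infer a fixed loss of power for a blunted response. The protocol does not support one. The loss is nil at rho 0, reaches about 60 points only with equal SDs and rho 0.7, is small when unstimulated wells vary little, and reverses at low correlation when several stimulants are pooled. The protocol fixes neither these quantities nor the layout of the stimulation factor.

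The point does not extend to the bacterial killing and migration assays. It should be settled before the Aim 2 data are analysed.

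**What to change.** Amend Section I, C.c to say that:

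- the Aim 2 cytokine test is the within-participant treatment-by-stimulation contrast at the altitude days, separately for LPS and for R848, on a stated scale. On the log scale the contrast is a ratio of fold changes. The choice matters, because an equal proportional fall in both wells leaves the log contrast at zero but shrinks the raw increment;
- follow-up is not restricted to significant main effects;
- the AZ effect is reported separately for stimulated and unstimulated wells, so that a change confined to unstimulated wells is not read as altered responsiveness.

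The cost is a few sentences; the samples, wells and assays are unchanged. There are two small downsides. The contrast can have less power than the pooled average when wells are weakly correlated and several stimulants are pooled. Analytes below detection in unstimulated wells also need a stated floor before logs or differences are taken.
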